Most patients receiving PDT experience pain during irradiation. In Dundee, 16% of 4717 PDT treatments were associated with severe pain [4]. This limits successful and effective delivery of PDT and negatively impacts on the patient's experience of treatment. Unsurprisingly, given the nature of pain transmission, PDT is most painful in patients when performed on highly innervated skin such as the face and scalp [5, 13]. Interestingly, higher pain levels are experienced during PDT for AK and psoriasis than for basal cell carcinoma [13, 14], perhaps implicating neuromodulatory factors released from specific cell types. Characteristics of irradiation (emission spectrum and irradiance) appear to influence the perception of pain. Red light produces more pain than violet light and pain appears to correlate with the rate of photobleaching of PpIX [15, 16]. Reduction of irradiance may reduce pain but greatly increases treatment times [6, 7]. Other options for pain relief are limited as conventional non-invasive methods, such as topical analgesia with morphine or local anaesthetics are not significantly effective [5, 17, 18]. Local anaesthetic nerve block results in effective pain reduction [19] but is invasive, not feasible at all body sites and there may be risk of toxicity. Cooling is associated with slight reduction in PDT-induced pain [20], although there are concerns that this may reduce the efficacy of PDT [21].

Mechanisms of PDT pain

A randomised double blind, placebo controlled study of the efficacy of topical menthol for pain relief during topical photodynamic therapy

v.6.0 27/March/2019

Little is known about the mechanism(s) of PDT-induced pain. At the time of writing a literature search using the terms “pain and photodynamic therapy” yielded 423 publications, although most relate to the prevalence of PDT-pain and the limited success of treatment. Inhibition of PDT-induced pain by nerve block [19] implicates classical modes of pain transmission in which voltage activated sodium channels (VASCs) are activated leading to action potentials in primary afferent fibres stimulating ascending pain pathways in the spinal cord, thalamus and cortex [22]. PDT pain is described as a burning sensation. Furthermore, demonstrations that cooling reduces PDT pain may implicate heat-sensitive nociceptors. The transient receptor potential (TRP) family of ion channels senses heat, among other noxious stimuli including the pungent vanilloid capsaicin [23].

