2.1.2 Secondary Objectives

We will also examine possible differences in phototoxicity of the two regimens and assess patient evaluation of treatment. We will additionally assess fluorescence after cream application and before irradiation, using Wood's light as used in routine clinical practice. Efficacy of the two treatment regimens will also be assessed.

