2.2.2. Secondary Outcomes

Phototoxicity as assessed by semi-quantitative scoring of erythema, oedema and urticaria will be assessed immediately after irradiation. Fluorescence will also be assessed after Ameluz and IMP applications using Wood's light. Efficacy of treatment (clearance, partial or no response) three months after PDT will be determined clinically. Patient evaluation of treatment will also be assessed.

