A study clinician, technologist or nurse will obtain a medical history and the areas for treatment will be examined, the study fields will be marked out, lesions counted and the fields mapped and photographed. The maximal diameter of each comparable field will be 5x10cm. Topical PDT will be undertaken using the standard Ameluz[®] PDT regime (11). In brief, any hyperkeratotic areas will be surface prepared using a disposable ring curette (Stiefel[™]), without the need for local anaesthesia. Ameluz[®] gel will be thinly applied to both comparative fields, left to dry and occluded for three hours with Tegaderm and Mepore dressings. After removal of the dressings and surplus gel, the active treatment (menthol 5% in aqueous cream) or placebo (aqueous cream) will be applied to right/left side according to randomisation. The IMPD/placebo will be provided as 1g in 2mL syringes, applied to the maximum field size field of 5x10cm or pro-rata to smaller field sizes. Ten minutes later any excess cream will be wiped off and irradiation will commence (LED 37.5 J/cm², irradiance approximately 80 mW/cm²), with the randomisation to account for which side will be treated first. Menthol vapour will be in the room in order to mask the vapour of the IMP and to aid with ensuring blinding of both patient and assessor (research nurse or another technologist).

Assessments

Fluorescence will be examined using a semi-quantitative scoring system (0=none; 1=minimal; 2=moderate; 3=strong) after 3 h of Ameluz application and after menthol/placebo application.

Pain scores will be recorded by the patient immediately after irradiation (as recall of maximal pain experienced during irradiation) and at 3, 6 and 24 h after irradiation

A randomised double blind, placebo controlled study of the efficacy of topical menthol for pain relief during topical photodynamic therapy

[figure not shown]
v.6.0 27/March/2019

using a VAS score of 0-10cm at each time-point. The study technologist or research nurse will be present at the time of the first pain score but patients will fill in the VAS scores themselves at home for the 3, 6 and 24 h time-points and send these back to the PDT clinic by stamped addressed envelope. A study nurse will contact the patient by phone at one week, to ask about any adverse effects and to check that the VAS scores are returned.

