Phototoxicity will be assessed by the study technologist or research nurse immediately after irradiation using a semi-quantitative scoring system for erythema (0=none; 1=mild; 2=moderate; 3=severe), oedema (1=yes; 0=no), exudation (1=yes; 0=no) and urticaria (1=yes; 0=no).

[figure not shown]
Efficacy will be assessed clinically approximately three months (\pm 2 weeks) after PDT, with clearance, partial response or no response recorded as outcomes. Patient evaluation of treatment and of blinding will also be assessed for each treatment site when the patient returns their pain scores after 24h, using the following two questions: [1] Which side do you think received menthol? Right/left/not sure; [2] Which side do you think was best? Right/left/no difference.

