9 STATISTICS AND DATA ANALYSIS

9.1 SAMPLE SIZE CALCULATION

We were not able to obtain variance for within-subjects pain differences from similar studies. An assessment of pain experience with PDT in our unit found a standard deviation of between subjects VAS pain score of 2.7cm. Rounding this up to 3cm and conservatively estimating that within-subject's pain score SD will be two-thirds of this (2cm) then we estimated that 21 subjects should give us 90% power to detect a mean difference in VAS scores of 1.5 cm as significant at the 5% level. To allow for dropouts, assuming dropout rate by 3 months of up to 30%, we will recruit 30 subjects.

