9.2 PROPOSED ANALYSES

The main analysis will be the difference between within-subject pain using appropriate paired methods (paired Student's t-test if assumptions met). The difference will be expressed with 95% confidence interval. VAS scores immediately after PDT and the areas under the curve for pain scores plotted over each of the time points will be assessed. Within subject comparisons of fluorescence, phototoxicity, efficacy and patient evaluation will be secondary outcome measures, using paired statistical analyses.

Amendment

Since the original concept and set up of the study, there have been changes in the practice of PDT for AKs on the face and scalp, with low illuminance daylight PDT now favoured when practicable because this form of PDT is less painful than conventional PDT. Therefore, we will perform (statistical analysis by someone not involved in patient treatments and assessments, to ensure blinding) an interim analysis. With the same assumptions as before with a power of 90% we expect to detect a difference (at alpha = 0.1 level, two tailed testing) of 3 cm or more (on VAS) in pain between groups with 9 subjects should such a difference exist. We will therefore recruit a minimum of 9 participants and if on this interim analysis such a difference is detected then the study will be continued as originally planned in order to determine whether the difference can be detected at alpha = 0.05 level of significance, unless the dermatologist analysing the data advises stopping early as a greater difference already detected. If it seems unlikely that there will be a difference of ≥ 3 cm in pain

A randomised double blind, placebo controlled study of the efficacy of topical menthol for pain relief during topical photodynamic therapy

v.6.0 27/March/2019

on VAS based on this interim analysis, then (with the changes in use of PDT for AKs on face and scalp) the data analyst will advise stopping the study.

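### Lesions are counted and mapped at baseline but three-month efficacy is scored only in three categories, which weakens the comparison for moderate losses of PDT efficacy

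*Combined protocol and SAP*

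**What the plan says.** On the treatment day, section 3.1 states that "the study fields will be marked out, lesions counted and the fields mapped and photographed". At about three months the same section records efficacy "with clearance, partial response or no response recorded as outcomes". Section 2.2.2 agrees: "Efficacy of treatment (clearance, partial or no response) three months after PDT will be determined clinically". The study matrix in section 3.3 lists one efficacy assessment at that visit and nothing more. No cut-offs are given for the categories, no repeat count is planned, and no margin is set.

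Section 2.1.2 makes this a secondary objective: "Efficacy of the two treatment regimens will also be assessed". Section 9.2 gives the analysis in one sentence: "Within subject comparisons of fluorescence, phototoxicity, efficacy and patient evaluation will be secondary outcome measures, using paired statistical analyses". No test is named. The sample size in section 9.1 rests on pain alone. The amendment text in section 9.2 adds an interim analysis after a minimum of 9 participants, at which the study may stop.

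**The concern.** The trial is meant to inform whether menthol enters routine PDT regimens (opening summary and section 1.2). That depends on pain, but also on PDT still working. The three-month visit is the only direct check in patients that it does. Section 1.1 shows that the authors know the issue: of cooling, another way to relieve PDT pain, they write that "there are concerns that this may reduce the efficacy of PDT".

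A three-level scale is coarse for this purpose. If one side goes from 8 lesions to 1 and the other from 8 to 4, both are naturally scored as partial responses, and the patient contributes no difference. The baseline count and map that would separate the two sides already exist. With so few patients, discarding that information is costly.

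**Working it through.** **Reproducing the plan's figure.** Section 9.1 seeks 90% power to detect "a mean difference in VAS scores of 1.5 cm as significant at the 5% level", with a within-subject SD of 2 cm, here taken as the SD of the paired difference. The noncentrality is δ/(σ/√n) = 1.5/(2/√21) = 3.44, and a two-sided 5% paired t-test gives 90.5% power (n = 20 gives 88.9%). So n = 21 reproduces, and 21/0.7 = 30 recruited. Pain is last scored at 24 hours, whereas the dropout allowance runs to three months. The 21 completers are therefore the patients available for efficacy.

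**What a categorical paired test needs.** Ties drop out of an exact sign or McNemar test. Five discordant patients all in one direction give p = 2 × 0.5⁵ = 0.0625; six give 2 × 0.5⁶ = 0.031. At least 6 discordant patients are needed, and with 6 to 8 all must favour the same side. For complete clearance (yes/no), 21 patients and within-patient correlation 0 to 0.5, exact power is:
- 80% vs 70%: 4–5%
- 80% vs 60%: 18–23%
- 80% vs 50%: 39–64%

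With 9 patients these are at most 0.5%, 2% and 6%.

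**Categories against counts.** Model: lesions cleared on side s of patient i are binomial, with logit(p) = α_s + u_i + e_is. Each α_s is set so that average clearance equals the stated value. Assumptions, none of them in the documents: lesions per side vary about a mean of 4 or 8; SD of u is 1.0 or 1.5; SD of e is 0.5; all lesions cleared is clearance, none cleared is no response, anything between is partial. Entries are power in %, with the range taken over the settings (3,000 runs each).

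| Average clearance, placebo to menthol | Sign test on categories, n = 21 | Paired t on proportion cleared, n = 21 | Sign test, n = 9 | Paired t, n = 9 |
|---|---|---|---|---|
| 85% to 75% | 13–15 | 27–52 | 1–2 | 13–19 |
| 75% to 60% | 14–22 | 43–73 | 0–4 | 19–34 |
| 85% to 65% | 44–51 | 73–96 | 4–7 | 34–59 |
| 85% to 55% | 73–84 | 94–100 | 9–22 | 61–87 |

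Repeat runs move the edges by a few points. For the first two rows they give 11–23% against 27–74% at 21 patients, and an upper edge of 36% for counts at 9. The upper edge of the sign test for the 30-point loss becomes 87%.

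The starting level matters. A fall from 85% to 70% is also 15 points, and there (4 to 8 lesions, patient SD 1, side SD 0 to 1) the sign test gives 28–34% and counts 50–92%.

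**Is the gap only the choice of test?** The exact sign test is conservative: its true type I error is about 2%, against 4–5% for the t-test. Using the same paired t-test on the three-level score (patient SD 1) raises categorical power to 25–35% in the first two contrasts and to 40–48% for 85% to 70%. Over a wider grid for losses of 10 to 15 points (4, 6 or 8 lesions, side SD 0, 0.5 or 1), the t-test gives 21–48% on the score and 30–92% on the proportion. Counts were better in every setting; the narrowest gap was 24% against 30%. Between 51% and 77% of pairs tied on the categories.

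**The case against.** Efficacy is an unpowered secondary outcome. No margin is set and no conclusion of preserved efficacy is planned, so much of the weakness comes from 21 patients and not from the scale. That stands: for a 10-point loss, counts also reach only 27–52%.

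Part of the gap is the sign test, which section 9.2 does not name. A mid-p version on the categories would give 45% (6 lesions) and 42% (8 lesions) for 85% vs 70% without side variation, against 34% and 29% for the exact test. That stands too, but counts give 84% and 92% in the same settings.

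The simulation assumes error-free counts. Section 3.1 lets a clinician, technologist or nurse examine the patient at baseline, and nothing says who would recount. Recount error or new lesions would reduce the advantage. The baseline map and photographs also have some use already, as the reference for judging response, and the CRF, which is not in the documents, may hold a recount. The protocol does not plan one.

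A reader might infer three stronger things. The first is that the trial is close to blind to a loss of efficacy. At the planned size it is not: the categories detect a 20-point loss in about half of trials and a 30-point loss in about 73–87%. The second is that most fields will be scored partial. The documents give no basis for this; with 85% average clearance and 4 lesions, about 60% of placebo fields clear completely. The third is that the protocol suspects menthol of reducing efficacy. Section 1.1 voices that concern for cooling. Menthol is described as causing a cooling sensation, and 16% menthol left PpIX fluorescence in mice unchanged. Fluorescence is only indirect evidence on clinical clearance.

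**Conclusion.** The point holds for moderate losses, and more strongly if the study stops early. Under the stated assumptions, with 21 completers and a fall from 85% to 75% or from 75% to 60%, the sign test on the categories has about 11–23% power and the paired difference in proportion cleared about 27–74%. Near 9 patients it is about 0–4% against 13–36%, and even a 30-point loss would be found on the categories in at most about 22% of trials. Stopping early for a large pain effect is allowed, so menthol could look worth adopting when the efficacy comparison says almost nothing.

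The size of the gain depends on lesion numbers, clearance rates and side-to-side variation that the documents do not give; its direction did not change in any setting tried. Counts would not make efficacy a powered outcome. This is a worthwhile low-cost improvement and does not affect the pain analysis.

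**What to change.** At the existing three-month visit, have one blinded assessor, the same for both sides and preferably the person who made the baseline count, count the remaining baseline lesions in each mapped field with the map and photographs to hand. New lesions are recorded separately. In section 9.2, make the main efficacy measure the within-patient difference in percentage of baseline lesions cleared, with a 95% CI (paired t-test or signed-rank), and label it as unpowered. Define the three categories and keep them as a descriptive summary.

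The cost is a few minutes per patient at a visit that already takes place, one CRF field per side, a sentence in section 9.2 and matching wording in sections 2.2.2 and 3.1. The drawback is some recount error, which using the same assessor and the map limits but does not remove.

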3.3 STUDY MATRIX

| ACTIVITY | Day 1 | Day 2 | DAY 8 | Approx. 3 months |
|--|-------|-------|-------|------------------|
| Informed consent | √ | | | |
| Eligibility screening | √ | | | |
| Standard skin preparation for PDT | √ | | | |
| Application of IMP/placebo (remove after 10 minutes) | √ | | | |
| PDT irradiation | √ | | | |
| Pain assessment (visual analogue scores) by subject immediately after PDT - clinic | √ | | | |
| Fluorescence assessment by technician | √ | | | |
| Phototoxicity assessment by technician | √ | | | |
| Pain assessment (visual analogue scores) by subject 3hrs after PDT - home | √ | | | |
| Pain assessment (visual analogue scores) by subject 6 hrs after PDT - home | √ | | | |
| Pain assessment (visual analogue scores) by subject 24 hrs after PDT - home | | √ | | |
| Follow-up phone call by research nurse | | | √ | |
| Assessment of treatment efficacy at 3 months after PDT | | | | √ |
| Patient evaluation of PDT & blinding | | √ | | |

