5.5.3 Blinding and Emergency Unblinding Procedures

Those assessing patients (Consultant Dermatologist, study technologist or research nurse) will not be aware of which side has received which intervention. It is possible that all patients (from sensation [cooling] of menthol) might not remain fully blinded. Patients will be instructed not to tell those assessing them if they suspect they know which intervention is applied to each side. After treatment, patients will be asked to provide an opinion as to which treatment was applied to each side to allow assessment as to how complete patient blinding was.

Given the nature of the study, it is very unlikely that unblinding will be required. If required, it will be conducted by a PBU member of staff unconnected to the trial.

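### The only patient blinding question comes after 24 h of pain scoring, so if menthol works, correct guesses only partly separate loss of blinding from pain relief

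*Combined protocol and SAP*

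**What the plan says.** Section 3.1 collects the blinding guess once: "Patient evaluation of treatment and of blinding will also be assessed for each treatment site when the patient returns their pain scores after 24h". The item reads "Which side do you think received menthol? Right/left/not sure", and the item after it reads "Which side do you think was best? Right/left/no difference". The study matrix in 3.3 ticks the row "Patient evaluation of PDT & blinding" on Day 2 only. Pain has by then been scored immediately after irradiation (as recall of the worst pain) and at 3, 6 and 24 h.

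Section 5.5.3 says the guess is collected "to allow assessment as to how complete patient blinding was". It also concedes the likely route of failure: "It is possible that all patients (from sensation [cooling] of menthol) might not remain fully blinded". Section 6.1.6 expects a minor cooling or tingling on skin contact. In 3.1 the cream is on the skin before the light: "Ten minutes later any excess cream will be wiped off and irradiation will commence". Room vapour is used to mask the smell.

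No section asks for a guess earlier, asks why the patient guessed as they did, or says how the guesses will be analysed.

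**The concern.** The threat that 5.5.3 names can be felt before irradiation, but the question is put after a second cue has been added: which side hurt less. The trial's title says that menthol is being tested for pain relief, and 3.1 has the study described in full before consent. A patient who noticed neither cooling nor smell can therefore reasonably name the less painful side. If menthol works, that guess tends to be right, and it enters the tally alongside guesses from patients who recognised the cream.

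The primary outcome is the patient's own pain score, compared within patient against plain aqueous cream. After a positive result, the first question will be whether patients knew which side had menthol. The guess is the one item designed to answer that, and a positive result is the case in which it is hardest to read. Because no reason is recorded, later analysis can recover only part of the distinction.

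**Working it through.** **Inputs.** From 9.1: difference 1.5 cm, SD 2 cm, 21 patients, 90% power, 5% level (taken as two-sided), 30 recruited for up to 30% dropout. From the amendment in 9.2: a difference of 3 cm. Not in the documents: the share *f* of patients who guess from pain, which is varied below.

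**Reproducing the plan's figure.** A paired t-test (noncentral t, two-sided 5%) with difference 1.5 and SD of the differences 2 needs 21 patients; power at 21 is 90.5%. 21 / 0.7 = 30. If 2 cm were instead the SD on each side with independent sides, the SD of the difference would be 2 × √2 = 2.83 and 40 patients would be needed. The stated 21 therefore treats 2 cm as the SD of the paired difference, and that reading is used here.

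**Chance that the menthol side is the less painful one** (normal differences): p = Φ(difference / SD).
- 1.5 cm: Φ(1.5/2) = Φ(0.75) = 0.773
- 3 cm: Φ(3/2) = Φ(1.5) = 0.933

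**Correct guesses under a perfect blind.** Suppose nobody detects menthol by cooling or smell, nobody answers *not sure*, a share *f* names the less painful side and the rest guess at random. Then q = f·p + (1 − f)·0.5. For example, with f = 0.5 at 1.5 cm: 0.5 × 0.773 + 0.5 × 0.5 = 0.637.

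**How often such a group would look unblinded.** An exact two-sided 5% test of 21 guesses against 50% flags 16 or more correct. With q = 0.5 that happens in 1.3% of trials. The test is an illustration; the plan specifies none.

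| Share guessing from pain | 1.5 cm: correct | 1.5 cm: flagged (n = 21) | 3 cm: correct | 3 cm: flagged (n = 21) |
|---|---|---|---|---|
| All | 77% | 66% | 93% | 99.8% |
| Three quarters | 71% | 38% | 83% | 85% |
| Half | 64% | 17% | 72% | 43% |
| A quarter | 57% | 6% | 61% | 11% |
| None | 50% | 1.3% | 50% | 1.3% |

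With 30 patients (cut-off 21), the top-left case is flagged in 88% of trials. A perfectly blinded group asked before the light would be expected to guess 50% correctly at any effect size, that is 10.5 of 21, against 16.2 (1.5 cm) or 19.6 (3 cm) if all guess from pain at 24 h.

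**What the collected data can still separate.** A patient whose placebo side hurt less guesses wrongly if going by pain and correctly if going by cooling. The expected number of such patients out of 21 is 21 × (1 − 0.773) = 4.8 at 1.5 cm and 21 × (1 − 0.933) = 1.4 at 3 cm.

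**The case against.** A reader might infer that the 24 h question can show nothing about the blind, or that it reads the same whether the blind held or failed. The documents do not support that.
- A result near 50%, or many *not sure* answers (an option on the form), would be reassuring.
- If menthol has no effect on pain, the guesses still reflect cooling or smell.
- Universal detection gives 100% correct, while a perfect blind with everyone guessing from pain gives 77% at 1.5 cm. All 21 correct would then occur with probability 0.773^21 = 0.5%. At 3 cm it is 0.933^21 = 23%, so the check is weaker there but not empty.
- Scores by side are collected, so the guess can be set against the less painful side. The patients who tell the two routes apart are few (4.8 or 1.4 of 21), and expectation could reduce them further: someone who recognised menthol may score that side lower.

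A reader might also take 66% as the size of the problem. It is the top of the range for 1.5 cm and 21 patients. It needs every patient to guess from pain and none to answer *not sure*. If a third answered *not sure* (an assumption), leaving 14 guesses, it would be 35%.

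Finally, a reader might infer that asking for the menthol side first biases the preference item and that the two should be swapped. Nothing in the documents shows such steering, since both answers go back together. Swapping would make patients commit to the better side just before guessing, which may strengthen guessing from pain.

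These points limit the claim. They leave standing that, in a positive trial, the 24 h guess mixes two explanations and the form collects nothing on why a side was named.

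**Conclusion.** The point holds in limited form. If menthol reduces pain, a high rate of correct guesses at 24 h only partly separates loss of blinding from efficacy. Under a perfect blind, the expected rate of correct guesses at 1.5 cm runs from 57% (a quarter guess from pain) to 77% (all do), and the illustrative test flags 6% to 66% of trials with 21 patients. At 3 cm the ranges are 61% to 93% and 11% to 99.8%.

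These figures assume normally distributed paired differences with SD 2 cm, no *not sure* answers, and random guessing by patients who do not go by pain. The share guessing from pain is an assumption throughout. The matter affects how a positive result can be interpreted; the sample size and the primary analysis are unaffected. It is worth correcting because the correction costs almost nothing.

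**What to change.** In 3.1 and 5.5.3, keep the 24 h question and the present question order, and add one tick-all-that-apply line: *Why do you think so? Feeling before the light / smell / less pain / only a guess.* State in 5.5.3 that:
- guesses will be reported by reason;
- guesses citing a feeling before the light or smell will be treated as possible loss of blinding, whether or not less pain is also ticked;
- the guess will be cross-tabulated against the side with the lower VAS score.

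The cost is one extra line on a form that patients already return, plus one table. Self-reported reasons are imperfect, and patients may rationalise them afterwards, but the present form has no such information.

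A sealed question after the cream is wiped off and before irradiation would avoid the confounding with pain. It should be optional only, because it may draw attention to the cooling just before the primary pain score.
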